### **11.2 Adherence to the Protocol**

The investigator will conduct the study in strict accordance with the protocol (refer to ICH E6, Section 4.5).

### **11.3 Monitoring Procedures**

The sponsor's/CRO's CRA will maintain contact with the investigator and designated staff by telephone, letter, or email between study visits. Monitoring visits to each site will be conducted by the assigned CRA as described in the monitoring plan. The investigator (or if regionally required, the head of the medical institution) will allow the CRA to inspect the clinical, laboratory, and pharmacy facilities to assure compliance with GCP and local regulatory requirements. The CRFs and subject's corresponding original medical records (source documents) are to be fully available for review by the sponsor's representatives at regular intervals. These reviews verify adherence to study protocol and data accuracy in accordance with local regulations. All records at the site are subject to inspection by the local auditing agency and to IRB/IEC review.

In accordance with ICH E6, Section 1.52, source documents include, but are not limited to, the following:

- Clinic, office, or hospital charts

- Copies or transcribed health care provider notes that have been certified for accuracy after production
- Recorded data from automated instruments such as IVRS, x-rays, and other imaging reports (eg, sonograms, CT scans, magnetic resonance images, radioactive images, ECGs, rhythm strips, EEGs, polysomnographs, pulmonary function tests) regardless of how these images are stored, including microfiche and photographic negatives
- Pain, quality of life, or medical history questionnaires completed by subjects
- Records of telephone contacts
- Diaries or evaluation checklists
- Drug distribution and accountability logs maintained in pharmacies or by research personnel
- Laboratory results and other laboratory test outputs (eg, urine pregnancy test result documentation and urine dip-sticks)
- Correspondence regarding a study subject's treatment between physicians or memoranda sent to the IRBs/IECs
- CRF components (eg, questionnaires) that are completed directly by subjects and serve as their own source
- Electronic Patient-Reported Outcome by self-reported measures

#### **11.4 Recording of Data**

A CRF is required and must be completed for each subject by qualified and authorized personnel. All data on the CRF must reflect the corresponding source document, except when a section of the CRF itself is used as the source document. Any correction to entries made on the CRF must be documented in a valid audit trail where the correction is dated, the individual making the correct is identified, the reason for the change is stated, and the original data are not obscured. Only data required by the protocol for the purposes of the study should be collected.

The investigator must sign each CRF. The investigator will report the CRFs to the sponsor and retain a copy of the CRFs.

#### **11.5 Identification of Source Data**

All data to be recorded on the CRF must reflect the corresponding source documents.

#### **11.6 Retention of Records**

The circumstances of completion or termination of the study notwithstanding, the investigator (or if regionally required, the head of the medical institution or the designated representative) is responsible for retaining all study documents, including but not limited to the protocol, copies of CRFs, the Investigator's Brochure, and regulatory agency registration documents (eg, Form FDA 1572 for US sites), Investigator and Site Information Form (for non-US sites), ICFs, and IRB/IEC correspondence). The site should plan to retain study

documents, as directed by the sponsor, for at least 15 years following the completion of the study.

It is requested that at the completion of the required retention period, or should the investigator retire or relocate, the investigator contact the sponsor, allowing the sponsor the option of permanently retaining the study records.

## **11.7 Auditing Procedures and Inspection**

In addition to routine monitoring procedures, the sponsor's Clinical Quality Assurance department conducts audits of clinical research activities in accordance with the sponsor's SOPs to evaluate compliance with the principles of ICH GCP and all applicable local regulations. If a government regulatory authority requests an inspection during the study or after its completion, the investigator must inform the sponsor immediately.

## **11.8 Handling of Study Drug**

All study drug will be supplied to the principal investigator (or a designated pharmacist) by the sponsor. Drug supplies must be kept in an appropriate secure area (eg, locked cabinet) and stored according to the conditions specified on the drug labels. The investigator (or a designated pharmacist) must maintain an accurate record of the shipment and dispensing of the study drug in a drug accountability ledger, a copy of which must be given to the sponsor at the end of the study. An accurate record of the date and amount of study drug dispensed to each subject must be available for inspection at any time. The CRA will visit the site and review these documents along with all other study conduct documents at appropriate intervals once study drug has been received by the site.

All drug supplies are to be used only for this study and not for any other purpose. The investigator (or site personnel) must not destroy any drug labels or any partly used or unused drug supply before approval to do so by the sponsor. At the conclusion of the study and as appropriate during the study, the investigator (or a designated pharmacist) will return all used and unused drug containers, drug labels, and a copy of the completed drug disposition form to the sponsor's CRA (or designated contractor) or, when approval is given by the sponsor, will destroy supplies and containers at the site.

## **11.9 Publication of Results**

All manuscripts, abstracts, or other modes of presentation arising from the results of the study must be reviewed and approved in writing by the sponsor in advance of submission pursuant to the terms and conditions set forth in the executed Clinical Trial Agreement between the sponsor/CRO and the institution/investigator. The review is aimed at protecting the sponsor's proprietary information existing either at the date of the commencement of the study or generated during the study.

The detailed obligations regarding the publication of any data, material results, or other information generated or created in relation to the study shall be set out in the agreement between each investigator and the sponsor or CRO, as appropriate.

## **11.10 Disclosure and Confidentiality**

The contents of this protocol and any amendments and results obtained during the study should be kept confidential by the investigator, the investigator's staff, and the IRB/IEC and will not be disclosed in whole or in part to others, or used for any purpose other than reviewing or performing the study, without the written consent of the sponsor. No data collected as part of this study will be used in any written work, including publications, without the written consent of the sponsor. These obligations of confidentiality and non-use shall in no way diminish such obligations as set forth in either the Confidentiality Agreement or Clinical Trial Agreement executed between the sponsor/CRO and the institution/investigator.

All persons assisting in the performance of this study must be bound by the obligations of confidentiality and non-use set forth in either the Confidentiality Agreement or Clinical Trial Agreement executed between the institution/investigator and the sponsor/CRO.

## **11.11 Discontinuation of Study**

The sponsor reserves the right to discontinue the study for medical reasons or any other reason at any time. If a study is prematurely terminated or suspended, the sponsor will promptly inform the investigators/institutions and regulatory authorities of the termination or suspension and the reason(s) for the termination or suspension. The IRB/IEC will also be informed promptly and provided the reason(s) for the termination or suspension by the sponsor or by the investigator/institution, as specified by the applicable regulatory requirement(s).

The investigator reserves the right to discontinue the study should his/her judgment so dictate. If the investigator terminates or suspends a study without prior agreement of the sponsor, the investigator should inform the institution where applicable, and the investigator/institution should promptly inform the sponsor and the IRB/IEC and provide the sponsor and the IRB/IEC with a detailed written explanation of the termination or suspension. Study records must be retained as noted above.

## **11.12 Subject Insurance and Indemnity**

The sponsor will provide insurance for any subjects participating in the study in accordance with all applicable laws and regulations.

## 12 APPENDICES

### Appendix 1      **Response Evaluation Criteria in Solid Tumors (RECIST) 1.1**

Tumor response assessments in this clinical study will use Response Evaluation Criteria in Solid Tumors (RECIST 1.1) based on the 2009 article by Eisenhauer et al entitled *New Response Evaluation Criteria in Solid Tumors: revised RECIST guideline (version 1.1)* ([Eisenhauer, et al., 2009](#)).

The sole modification to RECIST 1.1 to be implemented in this study is that chest x-rays may not be used to follow disease; only CT scans may be used to follow chest disease. As required by RECIST 1.1, the protocol states that the minimum duration of stable disease is 7 weeks following the date of first dose of study drug.

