## Assessments

### Efficacy Assessments

Tumor assessment will be performed based on RECIST 1.1. Investigator-determined response assessments will be performed at each assessment time point and entered onto the case report form (CRF). Copies of all tumor assessment scans will be sent to an imaging core laboratory (ICL) designated by the sponsor for efficacy assessment and for confirmation of PD. Tumor assessments will be carried out following the guidelines provided by the ICL.

During the Screening Period, tumor assessments of the chest, abdomen, pelvis, and other areas of known disease or newly suspected disease should be performed within 28 days prior to Cycle 1 Day 1. A brain scan (CT scan with contrast or MRI pre- and post-gadolinium) will be performed at screening as clinically indicated, and thereafter during the study as clinically indicated. Historical CT or MRI scans performed within 28 days prior to Cycle 1 Day 1 may be used as screening scans (baseline scans) to demonstrate eligibility, as long as they meet minimum standards as separately defined by the ICL.

If available, bone imaging obtained within 8 weeks prior to Cycle 1 Day 1 should be sent to the ICL. Bone lesions noted on the screening/baseline images should be followed as non-target lesions with modalities other than nuclear medicine scans.

Tumor assessments will then be performed every 6 weeks  $\pm 1$  week following the date of randomization until Week 18. Following completion of the chemotherapy treatment period (ie, after Week 18), the frequency of tumor assessments will be every 9 weeks  $\pm 1$  week until Week 54  $\pm 1$  week. Thereafter, they will be performed every 12 weeks  $\pm 2$  weeks until documentation of PD (please see [schedule of assessments](#) for details). At any point, the CT/MRI scan should be performed earlier than the scheduled time point, if clinically indicated. After data cutoff for the primary analysis, tumor assessments should be performed following the prevailing local standard of care.

Disease progression per RECIST 1.1 during the randomization phase must be confirmed by IIR prior to the investigator discontinuing study treatment.

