#### **Sample Size Rationale**

A total sample size of 72 subjects is estimated for the primary efficacy endpoint of PFS. Assuming a hazard ratio of 0.4 (median PFS of 3.5 and 8.75 months for the control arm and the test arm, respectively), a one-sided type 1 error rate of 0.025, and power of 80%, 38 PFS events are required for the primary analysis. The total sample size of 72 subjects is estimated to achieve 38 PFS events assuming the analysis occurs approximately 32 months after the first subject is randomized (assuming a 20-month enrollment period), and accounts for a dropout rate of up to 40%.

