- Treatment Phase:** Tumor assessments of the chest, and other areas of known disease at Screening or newly suspected disease should be performed every 6±1 weeks from the date of randomization until Week 18±1 week, then every 9±1 weeks until Week 54±1 week, and thereafter, every 12±2 weeks until documentation of PD during the Treatment Phase (or sooner if there is evidence of progressive disease) and should utilize the same methodology (CT or MRI) and scan acquisition techniques (including use or nonuse of IV contrast) as was used for the screening assessments. Tumor response will be assessed according to RECIST 1.1. Any CR or PR must be confirmed not less than 4 weeks following the initial achievement of the response. **Off-Treatment:** Tumor assessments at the Off-Treatment Visit (within 1 week of the Off-treatment Visit) are only necessary for subjects who discontinue study treatment without disease progression, if more than 4 weeks have passed since the previous assessment and if the subject will not continue with follow-up scans.
- Follow-up:** For subjects who discontinue study treatment without disease progression, tumor assessments should continue to be performed according to the schedule: every 6±1 weeks until Week 18±1 week, then every 9±1 weeks until Week 54±1 week, thereafter, to be performed every 12±2 weeks, until documentation of progression or start of a new anticancer agent.
- r. Brain CT with contrast or MRI pre- and post- gadolinium contrast will be performed at the Screening Visit as clinically indicated, and thereafter during treatment as clinically indicated. For subjects with protocol-eligible treated brain metastases, brain CT/MRI will be performed at all tumor assessment time points.
- s. Height will be assessed at the Baseline Visit, Day 1 of every 4 cycles during the Treatment Phase, at the Off-treatment Visit and every 3 months during the Post-treatment Follow-up. Assessment of height in Post-treatment Follow-up is not required once pubertal development is complete. Proximal tibial growth plate x-rays should be conducted for subjects aged <18 years at baseline and at the Off-treatment Visit. If the growth plates are closed at baseline

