#### 9.7.1.1.3 EXPLORATORY ENDPOINTS

- Duration of response (DOR) by IIR and investigator assessment is defined as the time from the date a response was first documented until the date of the first documentation of PD or date of death from any case.
- Disease control rate (DCR) by IIR and investigator assessment is the proportion of subjects who have a best overall response of CR or PR or stable disease (SD). In this context, stable disease is defined as stable disease at  $\geq 7$  weeks after randomization to be considered best overall response.
- Clinical benefit rate (CBR) by IIR and investigator assessment is the proportion of subjects who have best overall response of CR or PR or durable SD (duration of SD  $\geq 23$  weeks after randomization).
- Efficacy endpoints (PFS, PFS-4m, PFS-1y, ORR-4m, and ORR) evaluated based on investigator assessment
- Proportion of subjects who achieve complete removal of baseline lesions and the proportion of subjects with unresectable baseline lesion(s) that are converted to resectable between the 2 treatment arms.
- Blood and tumor biomarkers will be assessed for identifying potential correlation with clinical outcomes-related endpoints.

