#### 9.7.1.6.2 EXPLORATORY EFFICACY ANALYSES

Median DOR by IIR among responders for each arm will be presented along with its corresponding 2-sided 95% CIs. Disease Control Rate (DCR) and CBR by IIR will be summarized and compared between arms using the same approach as for ORR. Efficacy endpoints PFS, PFS-4m, PFS-1y, ORR-4m, ORR, DOR, DCR, and CBR evaluated based on investigator assessment will be analyzed using the same approach as for the endpoints assessed by IIR.

The difference in the proportion of subjects who achieve complete removal of baseline lesion(s) and the proportion of subjects with unresectable baseline lesions(s) that are

converted to resectable between the 2 treatment arms and corresponding two-sided 95% CIs will be calculated.

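### The 7-week stable-disease rule behind the exploratory DCR does not fit the 6±1-week first scan and is given two different starting dates

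*Protocol*

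**What the plan says.** All of the following stands in the current Amendment 02 text.

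- **Endpoint definition.** The synopsis (Exploratory Endpoints) and Section 9.7.1.1.3 define DCR as the proportion with a best overall response of CR, PR or stable disease. For this purpose stable disease must be present at 7 or more "weeks after randomization to be considered best overall response".
- **Appendix 1.** The RECIST appendix reports the rule with another origin: "the protocol states that the minimum duration of stable disease is 7 weeks following the date of first dose of study drug".
- **Scan schedule.** Table 5, footnote q, sets assessments "every 6±1 weeks from the date of randomization until Week 18±1 week". The synopsis (Efficacy Assessments) and Section 9.5.1.2.1 agree. Unscheduled imaging is foreseen only as bringing a scan forward: "At any point, the CT/MRI scan should be performed earlier than the scheduled time point, if clinically indicated".
- **Responses.** CR and PR carry no 7-week minimum but need confirmation: "Any CR or PR must be confirmed not less than 4 weeks following the initial achievement of the response".
- **Use.** Section 9.7.1.6.2: "Disease Control Rate (DCR) and CBR by IIR will be summarized and compared between arms using the same approach as for ORR". The same analysis is repeated on investigator assessments.

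**The concern.** A minimum duration for stable disease has to work with the dates on which patients are scanned. Here the threshold sits on the last day of the first scan window. A site that scans on the nominal Week 6 date obtains a result that can never establish disease control. A site that misses the window and scans on day 50 obtains one that can. Two otherwise identical patients, each with stable disease at the first scan and progression at the second, are then treated differently, and the one scanned on schedule is the one who does not count.

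The two origins add a contradiction. Appendix 1 attributes to the protocol a rule that its endpoint sections do not contain. The wording differs too: Section 9.7.1.1.3 asks for stable disease at a time point, whereas Appendix 1 speaks of a minimum duration. If duration is taken to run until progression is documented, stable disease at Week 6 followed by progression at Week 12 passes Appendix 1 and fails Section 9.7.1.1.3.

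At stake are the meaning of an exploratory endpoint and the size of the arm difference reported on it.

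**Working it through.** The plan gives no expected DCR, so there is no figure to reproduce. The check is a count of days, followed by an estimate of size.

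**Inputs**

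- Threshold: 7 weeks = 49 days (Section 9.7.1.1.3 from randomization; Appendix 1 from first dose).
- Scan windows from randomization (Table 5, footnote q): first 6±1 weeks = days 35 to 49, which is 15 permitted days; second 12±1 weeks = days 77 to 91. Nothing is scheduled between Weeks 7 and 11.
- Planning assumption (synopsis, Sample Size Rationale): "median PFS of 3.5 and 8.75 months for the control arm and the test arm, respectively".

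**Step 1: randomization clock.** A first scan on day d qualifies if d ≥ 49. Within days 35 to 49 only d = 49 does, so 1 of 15 days (6.7%). If scan dates instead cluster around day 42, with an assumed standard deviation of 3 days, about 0.9% of in-window scans qualify. A scan on day 42 itself never does.

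**Step 2: first-dose clock.** With a lag of L days from randomization to first dose, the condition is d − L ≥ 49.

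| Lag L (days) | Qualifying in-window days |
|---|---|
| 0 | 1 of 15 |
| 1, 2, 3 or 7 | 0 of 15 |

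Table 5 appears to place randomization in the Cycle 1 Day 1 column, so the lag is probably short, but no maximum is stated.

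**Step 3: which scan decides.** The next scheduled scan that can establish stable disease falls on days 77 to 91. A Week 6 CR or PR must be confirmed at least 4 weeks later, in practice also at the Week 12 scan.

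**Step 4: size.** Assume exponential PFS, S(t) = 0.5^(t/median), with t in months = weeks × 7/30.4375. Six weeks is 1.380 months and twelve weeks 2.760 months.

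| | Arm B (median 3.5) | Arm A (median 8.75) | A minus B |
|---|---|---|---|
| S at 6 weeks | 0.5^(1.380/3.5) = 76.1% | 0.5^(1.380/8.75) = 89.6% | 13.6 points |
| S at 12 weeks | 0.5^(2.760/3.5) = 57.9% | 0.5^(2.760/8.75) = 80.4% | 22.5 points |

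(Differences are taken before rounding.) Between the two time points the proportion falls by about 18 points in Arm B and 9 in Arm A.

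**Step 5: aligned thresholds.** With a minimum of 5 weeks (day 35) from randomization, all 15 days of the first window qualify. With a minimum of 11 weeks (day 77), no in-window first scan qualifies and all 15 days of the second window do.

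**The case against.** The best defence is that 7 weeks is a choice. It is the end of the first window (6+1), and a minimum placed there asks stable disease to hold beyond the first assessment. That is coherent, and nothing in the protocol says that DCR should capture control at the first scan. This stands as far as it goes: a stricter endpoint is legitimate. It does not explain why one in-window day and any late scan should pass, and the protocol nowhere says that the Week 12 scan is required.

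A reader might also infer more than the text supports:

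- **That 18% of Arm B and 9% of Arm A are misclassified.** These figures are the gap between two definitions under assumed curves, not an error rate. They ignore missing or non-evaluable scans, response confirmation and the planned dropout of up to 40%.
- **That stable disease followed by progression is recorded as a best response of progression.** The protocol does not say so. It confines the 7-week rule to the DCR definition, and other response derivation may be set out elsewhere.
- **That DCR merely duplicates Week 12 PFS status.** CR and PR have no 7-week minimum, and a clinically indicated scan brought forward to between Weeks 7 and 11 could also establish stable disease.
- **That the two clocks often classify a patient differently.** The deciding scan would have to fall between the two 49-day marks, where almost no scheduled scan lies. The second clock removes the edge day and little else.
- **That a formal test is compromised.** DCR is exploratory; it is compared by a stratified difference with a 95% confidence interval, and no alpha is attached.

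**Conclusion.** The point holds, as a minor one. The protocol itself fixes the threshold, the origins and the scan dates, and they do not fit together, so this is not detail left to a SAP. The mismatch between threshold and window is the main defect: an on-time first scan qualifies on 1 of 15 days at most, while a late one qualifies. The conflicting origin in Appendix 1 is a real contradiction with little numerical effect.

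The expected arm difference is 13.6 points if the first scan counts and 22.5 if the second does. This rests on exponential PFS, on the planning medians, and on treating freedom from progression as a stand-in for DCR. PFS, PFS-4m, PFS-1y, OS, ORR, ORR-4m and the 38-event calculation do not use the rule and are unaffected.

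**What to change.** 1. Use randomization, which already anchors the scan schedule, as the single origin in the synopsis, Section 9.7.1.1.3 and Appendix 1, and use the same wording (stable disease at a time point, or a duration) in all three.
2. Tie the minimum to a scan window:
   - preferably 5 weeks or more after randomization, the lower edge of the first window, so that every on-time first scan can count; or
   - if a stricter endpoint is intended, state that stable disease must be shown at the Week 12 scan (11 weeks or more).
3. Make the choice before DCR is analysed, and align the imaging charter with it.

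The cost is a few wording edits and no new data. The 5-week option lets stable disease rest on a single scan, as early as day 35, is less strict, and under the planning curves gives the smaller expected arm difference. The Week 12 option keeps roughly what the present rule does in practice, but says so.
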